2.4.2 Administrator/Provider Measures

Administrator measures for baseline and 6 months include organization partnerships for depression, social risk factors and disaster services. We will also assess program size, services offered, aspects of organizational structure, and at follow-up, participation in planning and trainings.^{8,24,25} Provider or staff measures include time spent providing community services and intervention-relevant practices (e.g., problem-solving, screenings for depression, social risk factors, and disaster preparedness) (primary), and self and community efficacy to address stressors and disasters, and at baseline, training and job status.^{8,10,26} These measures have received Leadership Council and community stakeholder input.

2.5 Randomization

2.5.1 Program-level (CEP vs TA)

Within each community, programs will be matched based on a) range of services offered, b) clientele base (i.e. people with serious mental illness, formerly incarcerated people, etc.), c) program size, and d) existing partnerships or affiliations. “Affiliation” refers to having a strong referral relationship and/or clients within and across programs. Programs that match on multiple categories or identify that they are part of an existing partnership or affiliation will be paired. Matched pairs will fall within four different types of grouping:

- 1) Unique Program: There is no similar program to match with. Will be randomized independently.
- 2) Paired Program: Two programs that are similar in the criteria described above are paired and do not have affiliations with other programs in the study. One program is randomly assigned to one of the interventions. The other program will be assigned to the other intervention.

- 3) Unique Cluster: Programs that are affiliated with more than one other program. All programs in the cluster will be treated and randomized as one unit.
- 4) Cluster Pair: Two sets of clustered programs that are reasonably similar as a whole to each other. One cluster will be randomized to one of the interventions. The other cluster will be assigned to the other intervention.

By pairing programs following this schema, we reduce the chance of intervention contamination; that is, an individual client may receive services from multiple programs enrolled in the study. Community Investigators in the C-LEARN Leadership Council will review matching to ensure that programs are appropriately paired.

After matching, we will then randomize programs or program clusters using a random seed to TA or TA+CEP.^{24,27} All interventions are “encouragement” interventions. That is, participants are encouraged to consider interventions to which they are assigned, no one is forced to follow a given protocol. This is more of a public health rather than a clinical approach to intervention implementation.

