2.6.7 Power calculations

The power calculations were based on expecting a percentage point difference between groups ranging from 8 to 10. With enrolling 600 to 720 individuals per group (1200 to 1440 in total), 80% power was projected to detect the difference between groups ranging from 9.3% to 10.7% with alpha level of 0.05 (two-sided) and ICC=.01, allowed a retention rate of 65-75% at 6 months follow-up.²⁷ For outcome measures assessed monthly during the 6-month period, the proposed sample size with 60% retention is adequate for a between group difference of 7.3-7.9%.

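### For Aim 2, unpaired programs and unpaired clusters are randomized with no balance limit, so their sector mix and number per arm are left to chance; the precision cost is usually small.

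*Combined protocol and SAP*

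**What the plan says.** Section 2.5.1 of the Parts 1 and 2 protocol matches programs within each community on services, clientele, size and affiliations, and then defines four kinds of unit.

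- Paired Programs: "One program is randomly assigned to one of the interventions. The other program will be assigned to the other intervention".
- Cluster Pairs: "One cluster will be randomized to one of the interventions. The other cluster will be assigned to the other intervention".
- Unique Programs: "There is no similar program to match with. Will be randomized independently".
- Unique Clusters: "All programs in the cluster will be treated and randomized as one unit". Membership requires affiliation with more than one other program, so such a cluster has at least three programs. No maximum is given.

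The mechanism is described once: "After matching, we will then randomize programs or program clusters using a random seed to TA or TA+CEP". No allocation ratio, stratum, block or balance check accompanies it. The Leadership Council's community investigators review whether the pairing is appropriate, which is not the same as reviewing the balance of the resulting arms.

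Section 2.6.7 plans for equal groups: "With enrolling 600 to 720 individuals per group (1200 to 1440 in total), 80% power was projected". Section 2.6.2 expects at most 60 programs, up to 30 per community, and classes them as health or community. Section 2.5.2 randomizes the apps by individual client.

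**The concern.** Pairing protects the comparison only for units that find a partner. Those that do not are the unusual programs and the large affiliated groups, where a chance imbalance does most harm. A Unique Program carries its services and clientele to one arm. A Unique Cluster moves three or more programs on a single draw. If several unpaired units of one sector land together, sector and arm are partly mixed in the TA vs TA+CEP comparison.

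The analysis plan does not clearly deal with this. Section 2.7.2 controls for sector and community in the secondary program-level analysis. For client outcomes, which are the main analysis, 2.7.1 picks covariates from bivariate screening and does not commit to sector or community.

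Unequal arms also cost some precision. There is little to spare: 2.6.7 expects a difference of 8 to 10 points and can detect 9.3 to 10.7.

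**Working it through.** **1. The plan's own figure.** Inputs from 2.6.7: 600 or 720 per group, retention 65% or 75%, ICC 0.01, two-sided alpha 0.05, power 80%. Assumptions not in the documents: rates near 50%, and 30 programs per arm (60/2).

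Detectable difference d = (1.960 + 0.842) × √[0.25 × (1/n₁ + 1/n₂)], where n is the retained number divided by 1 + (m − 1) × 0.01 and m is retained clients per program.

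- 600 × 0.65 = 390; m = 390/30 = 13; design effect 1.12; n = 348; d = 10.6 points (plan 10.7).
- 720 × 0.75 = 540; m = 540/30 = 18; design effect 1.17; n = 462; d = 9.2 points (plan 9.3).

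The plan's range is reproduced, and it rests on equal arms.

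**2. Cost of unequal program numbers, if clients follow programs.** Inflation = √[(1/a + 1/b)/(2/30)].

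- 36:24: √[(1/36 + 1/24)/(2/30)] = 1.021, so 9.3–10.7 becomes 9.49–10.92.
- 40:20: √[(1/40 + 1/20)/(2/30)] = 1.061, so 9.3–10.7 becomes 9.86–11.35.

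**3. How often such splits occur.** The documents give no count or size of unpaired units, so each mix below is an assumption. There are 60 programs; pairs contribute no difference; each unpaired unit adds plus or minus its size with probability one half.

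| Unpaired units | Programs unpaired | 36:24 or worse | 40:20 or worse | Mean inflation of d |
|---|---|---|---|---|
| 12 single | 12 | under 0.1% | 0% | 0.2% |
| 12 single + 3 clusters of 4 | 24 | 17% | 0.5% | 0.9% |
| 12 single + 4 clusters of 5 | 32 | 32% | 8% | 1.7% |
| 10 single + 3 clusters of 8 | 34 | 38% | 24% | 3.1% |

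With 12 single programs and no clusters, 85% of draws leave the arms within 4 programs of each other. Clusters drive the imbalance.

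**4. Split by clients, total held fixed.** Formula of step 1; power is Φ(2.802 × D/d − 1.960), with D the plan's 10.7 or 9.3. The upper power values instead take a control rate of 0.50 with D added in the other arm.

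| Split | d, total 1200 | d, total 1440 | Power at D |
|---|---|---|---|
| 50:50 | 10.62 | 9.22 | 0.81 |
| 40:60 | 10.84 | 9.41 | 0.79–0.80 |
| 35:65 | 11.13 | 9.67 | 0.77–0.78 |
| 30:70 | 11.58 | 10.06 | 0.74 |

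Simulated chance that the smaller arm holds under 40% of clients (the range runs from equal program sizes to a between-program coefficient of variation of 0.6):

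- 30 pairs: 0–1%.
- 20 pairs and 20 single programs: 0–6%.
- 15 pairs, 15 single programs and 3 unpaired clusters of 5: 19–27%.
- 10 pairs, 10 single programs and 6 unpaired clusters of 5: 30–39%.
- 20 single programs and 4 unpaired clusters of 10: 59–60%.

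**5. Type of program.** If k unpaired units are of one kind, the chance that all fall in the same arm is 2 × 0.5^k: 25% for three and 12.5% for four. This does not depend on whether arm sizes come out equal.

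**The case against.** Matching is the main device in 2.5.1, and stakeholders review it. The cluster mixes in step 3 leave 24 to 34 of 60 programs unpaired (40–57%), which may be pessimistic; no document shows that a large unpaired cluster exists. Averaged over draws, the precision loss is 0.2–3.1%, and power stays near 0.80 at 40:60 if total enrolment is met. All of this stands, so the case cannot rest on power.

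Restriction also cannot balance a clientele served by only one program: that program must sit in one arm. Tight limits on several criteria, applied within each community to few units, could leave few admissible allocations. Both points stand and shape the fix.

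The hierarchical models in 2.7.1 allow covariates and compare unadjusted with adjusted coefficients, so adjustment for sector is possible. It is not committed to for client outcomes.

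A reader might infer that this rule is why 600–720 clients per group cannot be relied on. The documents do not support that. They set no client quota per program, so full pairing would not guarantee those numbers either. At a total of 1200, any departure from 50:50 puts one arm below 600, and that can happen with every program paired. A reader might also take all clusters to be drawn independently; cluster pairs go to opposite arms.

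**Conclusion.** The point holds for Aim 2 only. Unpaired programs and unpaired clusters are randomized without any stated balance limit, so the sector mix and number of programs among them are left to chance. Chance imbalance in the type of program is the main harm. Loss of precision is secondary: about 2% in detectable difference at 36:24, 6% at 40:20, and power about 0.74 at a 30:70 client split. It is material mainly when several large unpaired clusters fall together.

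How likely that is cannot be settled from the documents, because the number and size of unpaired units are not given; the frequencies above are a range over assumed mixes. The detectable differences also assume rates near 50% and 60 programs, which 2.6.2 gives as an upper figure. It would go too far to say that the trial is underpowered for this reason, or that the randomization is biased: each draw is still random.

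**What to change.** If the draw is still to be made, add a paragraph to 2.5.1. After pairs and cluster pairs are set, list the possible allocations of the remaining units in each community. Draw at random only from those that keep the arms within a stated difference on number of programs, expected client enrolment and the health/community class of 2.6.2. Set the limits loosely enough to leave many admissible allocations. The cost is a short script and a somewhat smaller allocation set, with no extra programs or clients. Imbalance is limited, not removed: a program with no analogue still sits in one arm, and one very large cluster may have no offset.

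The Introduction of the Part 3 protocol (May 25, 2020) describes Tier 1 randomization in the past tense and says the pandemic interrupted individual recruitment. If the draw is complete, a new rule comes too late. Then:

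- report the achieved TA vs TA+CEP split by programs, clients and sector, with the number and size of unpaired units;
- name sector and community as covariates in the Aim 2 client models in 2.7.2, rather than leaving them to bivariate screening;
- restate 2.6.7 for the achieved split, multiplying the equal-arm detectable difference by √[0.25/(p(1 − p))], where p is the share of clients in the smaller arm (p = 0.40 gives 1.021; p = 1/3 gives 1.061).

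This costs a table and two short text changes.

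### Section 2.5.1 has no rule that keeps two programs affiliated only with each other in the same arm

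*Combined protocol and SAP*

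**What the plan says.** Section 2.5.1 of the Parts 1 and 2 protocol matches programs within each community on services, clientele, size and existing affiliations (criteria a to d). Affiliation means a strong referral link, shared clients, or both. The general rule is: "Programs that match on multiple categories or identify that they are part of an existing partnership or affiliation will be paired". Four groups follow.

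- Item 1, Unique Program: "There is no similar program to match with. Will be randomized independently".
- Item 2, Paired Program, reads: "Two programs that are similar in the criteria described above are paired and do not have affiliations with other programs in the study". The allocation is: "One program is randomly assigned to one of the interventions. The other program will be assigned to the other intervention".
- Item 3, Unique Cluster, reads: "Programs that are affiliated with more than one other program. All programs in the cluster will be treated and randomized as one unit".
- Item 4, Cluster Pair: "Two sets of clustered programs that are reasonably similar as a whole to each other". The two sets go to opposite arms.

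The stated purpose is that by this scheme "we reduce the chance of intervention contamination; that is, an individual client may receive services from multiple programs enrolled in the study". Community Investigators on the Leadership Council "will review matching to ensure that programs are appropriately paired".

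**The concern.** Affiliation, as the section defines it, is the route by which a client of a TA program could be exposed to CEP. Affiliated programs should therefore share an arm. Item 3 is the only group that brings this about, and it asks for at least two affiliations. The smallest affiliated group, two programs linked only to each other, falls outside it.

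The contrast at stake is TA+CEP versus TA on the primary client outcomes (Aim 2). If a dyad is split, some clients analyzed under TA may also be served by a partner program running TA+CEP. Programs assigned to TA+CEP receive the TA materials anyway (section 2.3.2), so the leakage that matters runs from CEP into TA and pulls the intent-to-treat estimate towards the null. Section 2.7.1 plans no analysis that would reveal this. If dyads were instead kept together by judgment, this bias does not arise, but the allocation cannot be reproduced from the text.

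**Working it through.** **Step 1: put a dyad through each group.** Programs A and B are each affiliated only with the other.

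| Group | Does it apply to the dyad? | Chance of a split |
|---|---|---|
| Item 3 | No: one affiliation each, more than one required | 0 if it applied |
| Item 4 | No: needs existing clusters and gives no second definition of a cluster | not applicable |
| Item 2, where the affiliations ruled out are those outside the pair | Yes, if A and B are similar | 1 |
| Item 2, where the affiliations ruled out include the pair mate | No, and no other group names the dyad | undefined |
| Item 1 | Possible if A and B are not similar, since it has no affiliation condition; but the general rule says affiliated programs are paired | 0.5 (1:1 assumed) |

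No applicable route gives a split probability of 0. Under item 1, D dissimilar dyads give D/2 expected splits, and P(at least one) = 1 − 0.5^D: 50%, 75% and 97% for D = 1, 2 and 5.

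**Step 2: reproduce the plan's detectable difference.** Section 2.6.7 gives 600 to 720 enrolled per group, 65% to 75% retention, ICC 0.01, 80% power and two-sided alpha 0.05. Section 2.6.2 gives up to 60 programs. Assumed here: 30 equal-size programs per arm and an outcome proportion of 0.5.

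- Retained per arm: n = 600 × 0.65 = 390 to 720 × 0.75 = 540.
- Clients per program: m = n/30 = 13 to 18.
- Design effect: DEFF = 1 + (m − 1) × 0.01 = 1.12 to 1.17.
- SE = √(2 × 0.5 × 0.5 × DEFF / n) = 0.03789 to 0.03291.
- Detectable difference = (1.9600 + 0.8416) × SE = 10.62 to 9.22 points. The plan states 10.7% to 9.3%, so these assumptions come close.

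**Step 3: dilution if k dyads are split.** Each split dyad puts one program in TA. Let s be the share of that program's clients who get the full CEP effect through the partner. Full effect is an upper bound, since section 2.5.1 describes the interventions as encouragement only. The share of the contrast lost is s × k/30. Power for a true 10-point difference is Φ(0.10 × (1 − s × k/30)/SE − 1.96), shown for n = 390 and n = 540.

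| k | Lost, s = 25% | Power, s = 25% | Lost, s = 50% | Power, s = 50% |
|---|---|---|---|---|
| 0 | 0 | 75.1–86.0% | 0 | 75.1–86.0% |
| 1 | 0.8% | 74.4–85.4% | 1.7% | 73.7–84.8% |
| 2 | 1.7% | 73.7–84.8% | 3.3% | 72.3–83.6% |
| 5 | 4.2% | 71.5–82.9% | 8.3% | 67.7–79.5% |

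Fewer programs make each dyad weigh more: with 20 per arm, k = 2 loses 0.25 × 2/20 = 2.5% or 0.50 × 2/20 = 5.0%. The Part 3 protocol says the pandemic interrupted participant recruitment, so the achieved sample may be smaller than the planned one used here.

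**The case against.** The section claims only to reduce the chance of contamination. A scheme that holds larger clusters together does that without covering every dyad. Item 2 can be read to exclude a pair whose members are affiliated with each other, and on that reading no dyad is split on purpose. Item 1 sits badly with the rule that affiliated programs are paired, so the independent-randomization figures rest on a contested reading. The Community Investigators review the matching. No dyad is identified, the loss from one or two is small, and Tier 1 has already been randomized.

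Much of this stands as a limit on the consequence. Dyads may be absent, and one or two splits matter little. Five splits through item 1 would take about ten dyads in expectation; with five dyads, all five split only 0.5^5 = 3% of the time. Completed allocations cannot be changed.

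It does not close the gap. The reading that favors the plan leaves the dyad in no group. The other reading of item 2 is at least as easy to reach, because the phrase follows directly on two programs being paired, and it sends affiliated programs to opposite arms. The review has no stated same-arm criterion, and an appropriate pair could itself mean opposite arms.

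**Conclusion.** The concern holds. No group in section 2.5.1 ensures that two programs affiliated only with each other share an arm, and following the text can split them, against the section's stated purpose. That conclusion rests on the wording alone and is firm.

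The consequence is conditional and unquantified in the documents, which give neither the number of dyads nor the client overlap. Under the assumptions above, with one or two split dyads the Aim 2 contrast loses at most about 3% and power falls by less than 3 percentage points. Five split dyads with half the TA clients affected would cost about 8% of the contrast and 6.5 to 7.4 points of power. With no split dyads there is no bias, only an incomplete description of the allocation. It should be fixed because the check is cheap and bears on the interpretation of the Aim 2 comparison.

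**What to change.** 1. From the matching records made before randomization (criterion d), list every pair of programs affiliated only with each other and state whether it was split or kept in one arm. If there were none, say so; no further analysis is needed. Do not use partnerships reported at 6 months, because forming cross-sector relationships is an aim of CEP (section 2.3.2).
2. Only if any were split, add a sensitivity analysis of the Aim 2 effect that drops both members of each split dyad and keeps dyads held in one arm. Report the estimate with its confidence interval. Given a split, which member received TA+CEP is random, so the remaining comparison is still randomized. It supports the main analysis and does not replace it.
3. Correct the text, which also governs any program still to be randomized. Define a cluster as programs affiliated with *one or more* other enrolled programs, randomized as one unit. Limit item 1 to programs with no such affiliation. Allow opposite-arm pairing only for programs or clusters that are similar on criteria a to c and not affiliated with each other. The split probability for a dyad then becomes 0.

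**Cost.** One list, revised wording and at most one extra analysis. Merging k dyads gives k units of size 2m and 60 − 2k of size m, with effective size Σmᵢ²/Σmᵢ. Dropping k split dyads leaves n × (60 − 2k)/60 clients per arm, with m unchanged. Detectable differences, in points, for n = 540 and n = 390:

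| k | Merged | Dropped (sensitivity analysis) |
|---|---|---|
| 0 | 9.22–10.62 | 9.22–10.62 |
| 2 | 9.27–10.66 | 9.54–10.99 |
| 5 | 9.34–10.72 | 10.10–11.63 |
| 10 | 9.45–10.82 | 11.29–13.00 |

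Merging costs little. The sensitivity analysis is noticeably less precise when many dyads are dropped, which is another reason to keep it in a supporting role.

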2.5.2 Individual-level

Clients will be randomized at the individual level to receive one of the two mobile apps (CR or CR+eCBT), at the time of enrollment, using a random number generator method. A random number generator will be programmed in the CHORUS survey software.

2.6 Sampling

2.6.1 Communities

With stakeholder input, we will recruit services programs from New Orleans and Coastal South Louisiana. Racial and ethnic compositions of involved Louisiana communities are primarily African-American and Caucasian, with smaller populations of Latinos and also Vietnamese-Americans in coastal areas. The stakeholder Council has recommended specific communities with history of disaster exposure and diverse populations.

2.6.2 Programs

We will select eligible programs by combining program lists with community nominations, classifying programs as mental health, substance abuse, primary care/FQHCs/public health (health) or social services, community centers, parks and recreation community centers, businesses, salons, gyms, faith-based, and disaster preparedness/response programs (community).²⁸ We will invite programs through letters, phone calls and visits to recruit as many as 30 per community, expecting as many as 60 total programs.

2.6.3 Administrators and Providers/Staff

Each program will be asked to identify an administrator who will be invited to enroll and complete web-based surveys describing programs and partners at baseline and 6 month follow-up. Administrators will identify potentially eligible staff (full time, licensed or nonlicensed, but having direct client/community member contact) to be invited to enroll through meetings and

notices, anticipating 2-3 service providers or staff members per program to consent for surveys (N= up to 120 or more). Eligible staff may participate in trainings, tracked by sign-in logs, whether or not they participate in the survey subsamples.

2.6.4 Clients/ Community Members

Within enrolled programs we will invite adults ages 18 or older seeking services to complete self-or interviewer-administered eligibility screeners. Individuals will be eligible if they have access to a mobile device that receives short message service (SMS), screening positive in the last 6 months for exposure to social-risk factors (e.g., homelessness, below federal poverty level), disaster exposure or concern about future disasters; or depression by 8-item Patient Health Questionnaire (PHQ-8) score great than or equal to 10. We will exclude persons who: 1) do not provide contact information or do not have access to a phone with SMS-capability; 2) are severely cognitively impaired or intoxicated by survey-staff judgment; 3) are non-English speakers; 4) do not expect to live in South Louisiana over the following 12 months.

